4.8 Incentives and Compensation

Participants can be compensated individually up to \$245 for participation in the study.

- \$50 for completing a Baseline assessment
- \$20 for session 1
- \$20 for session 2
- \$25 for session 3
- \$20 for completing a 1-Month Follow-Up Assessment
- \$50 for completing a 3-Month Follow-Up Assessment
- \$60 for completing a 6-Month Follow-Up Assessment

4.9 Measures

-Table 1-	Construct	Measure
Screening information	Demographics	NHBS demographics inventory ⁷³
	Sexual HIV transmission risk	Self-Reported Sexual Behavior
	Problematic drug use	Drug Abuse Screening Test – 10 ⁷⁴
	Alcohol and Drug Use Behavior	NHBS Substance Use History Inventory ⁷³
	Intimate Partner Violence (IPV)	IPV among gay and bisexual men ⁷⁵
Individual functioning	Verification of couple status	Couples Verification Screener ⁶³
	Interpersonal Communication Skills	Interpersonal Communication Competence Scale ⁷⁶
	HIV knowledge	Brief HIV knowledge questionnaire ⁷⁷ *
	Pros and Cons of substance use	Decisional Balance - Club Drugs ⁷⁸
	Pros and Cons of Condomless sex	Decisional Balance - Unsafe Sex ⁷⁸
	Condom use skills/efficacy	Condom use self-efficacy scale ⁷⁹
	Condom attitudes/beliefs	Adapted condom attitudes scale ³⁰ *
	Anxiety and Depression	Brief Symptom Inventory ⁸⁰ (subscales)
	Experiences of stigma	Everyday discrimination ⁸¹
	Problematic alcohol use	Alcohol Use Disorders Identification Test (AUDIT) ⁸²
Dyadic functioning	Self-reported STI and HIV testing history; PrEP; and ART	
	Relationship satisfaction, cohesion, consensus & affectional expression	Dyadic adjustment scale ⁸³
	Partner communication strategies	Communication patterns questionnaire ⁸⁴
	Couples HIV Coping	Perceived severity of HIV infection ⁸⁵
		Preferences for sexual health outcomes ⁸⁵
		Couple efficacy to reduce HIV threat ⁸⁵
	Stigma directed at the relationship	Relationship marginalization ⁸⁶
	Relationship Control & Dominance	Sexual Relationship Power Scale (SRPS) ⁸⁷
Attitudes about Sexual Agreements	Sexual Agreement Investment Scale (SAIS) ⁸⁸	

5.0 CHP INTERVENTION/EDUCATION PROCEDURES

5.1 Intervention Design and Procedures

CHP is an intervention that utilizes motivational interviewing (MI) and personalized feedback to reduce CAS and substance use among partnered emerging adults. The CHP intervention will be delivered by MI-trained Clinical staff members. Participants will be randomized to receive the intervention during baseline appointment. The CHP intervention is comprised of 3 sessions. The intervention focuses on enhancing communication skills, and addressing drug use, risky sexual practices, couples HIV testing and counseling, PrEP and PEP, as well as navigation services to for PrEP for interested participants.

5.1.1 Three Sessions of CHP (Intervention)

Session	Objectives	Purpose	Method
Session 1			
1. Establish rapport		Facilitate intervention delivery	MI
2. Assess communication and problem solving skills		Determine the extent of skills training necessary	MI focused on: Communication challenges with others and then within the couple
3. Develop communication skills		Improve partner's ability to express and understand one another's attitudes, opinions and emotions	CBST
4. Develop explicit problem solving strategy		Improve partner's ability to effectively identify problems, generate and select solutions	CBST
5. Plan a date		Practice communication skills and increase positive dyadic interaction	Positive event scheduling
HOMework		Practice communication and problem solving skills. Go on a date.	
Session 2			
1. Assess use of skills and date completion		Assess successes and barriers to skill generalization	MI
2. Discuss mutual and individual goals		Assess the degree of dyadic dependence and broader goals and values	MI: Value's card sort completed jointly
3. Discuss the impact of substance use on goals		Identify potential areas in which substance use may interfere with broader individual and couple-level goals and values	MI
4. Establish substance use goals		Assess each partner's perception of ideal use for themselves and each other. In addition, identify ways in which partners can support goal achievement.	Mutual reinforcement training

5. Ongoing skill practice	Strengthen the use of effective communication and problem solving skills as applied in session.	MI and CBST
HOMEWORK	Practice communication and problem solving skills. Go on a date. Implement plan to achieve substance use goals.	
Session 3		
1. Assess use of skills and substance use goals	Assess successes and barriers to skill generalization	MI
2. Complete individual or couples HIV testing†	Establish sero-status and discuss joining sexual goals and risk reduction	CVCT or individual HIV testing and counseling
3. HIV medication adherence counseling††	Increase partner support for health-related behavior, particularly medication adherence	Life Steps
4. Establish a sexual agreement ††	Establish joint sexual goals and risk reduction	MI
5. Discuss links between substance use and sexual risk goals	Increase awareness of substance use and sex links	MI
5. Ongoing skill practice		MI and CBST
† Completed by HIV negative participants. Note: men in HIV negative seroconcordant couples will complete sexual agreement negotiation as part of CVCT.		
†† Completed by HIV positive participants and HIV negative participants in serodiscordant relationships.		
6. Relapse Prevention/Planning	Develop long-term goals for substance use, sexual behavior, and HIV risk reduction	MI Change planning
7. Termination	Summarize intervention work and conclude the intervention	

5.2 Three Sessions of Education

Session	Objectives	Purpose	Method
Session 1			Lecture + Question & Answers
	Introductions	What do we “want” in a partner? What do we “need” in order to get close?	
		What do couples “do” in relationships generally?	

Strategies to reduce HIV risk	
Session 2	Lecture + Question & Answers
Drug Use Education	Review the effects of several drugs on the brain and body Short term effects of drug use Long term effects of drug use
	Review the literature on drug use and sex
	Discuss drug and alcohol use in the gay community
	Review the effects of several drugs on the brain and body
Session 3	Lecture + Question & Answers + CHTC
Communication	Do's and Don'ts of Couples Communication
Couples HIV Testing and Counseling (CHTC)	Introduces testing Finger stick Sexual agreement Deliver test results
	Debrief

5.3 Sessions Training and Supervision

CHP Sessions training will occur prior to the initiation of Phase 2, with ongoing coaching, supervision and training of new therapists as well as educators, as required. The training manuals are located on appendix B for Intervention & CHTC and Appendix C for Educators.

Training for CHTC entails going through a series of trainings as well as mock sessions in order to get “Cleared” by clinical staff to conduct CHTC with participants. The same procedure will be followed for Educators, but they will be evaluated in their ability to present the education information and how to engage with the participant while avoiding the use of MI techniques.

5.4 Intervention Fidelity and Process Measures

We will assess the fidelity of CHP in two ways. First, CHP is an MI-based intervention. We will utilize the Motivational Treatment Integrity coding system, with additional codes relevant to MI with couples developed in our formative work, to evaluate fidelity to MI during the intervention. [name] is a member of the Motivational Interviewing Network of Trainers, and PRIDE maintains a staff of coders trained to use the system. We will MITI code 25% of CHP sessions. In addition, [name] will develop

a checklist based on the existing protocol which will be used to ensure that essential skills training components are completed.

5.5 Intervention & Education Monitoring and Supervision

All sessions (in-person based) will be audio-recorded, and one recording per facilitator will be randomly selected for MITI coding by the research team on a regular basis. Supervisors will complete fidelity checklists for the supervision session so the team can monitor implementation.

Education providers were trained by the project director or a trained clinical staff member. This involved a two-day workshop and subsequent mock deliveries of the education sessions. Educators were required to achieve fidelity to the protocol before delivering the condition to participants. The project director developed a session check-list that was approved by [name], which was used to determine fidelity. A trained clinical staff member reviewed each mock session and provided feedback. After being cleared to deliver the education condition to participants, a trained clinical staff member reviewed a minimum of 30% of completed sessions and provided feedback to education providers to ensure fidelity overtime.

CHP CHTC Supervisors: [name].

[figure not shown]
CHP Education Supervisors: [name]

6.0 SAFETY MONITORING PLAN

7.1 Data and Safety Monitoring Board

The study will be conducted under the supervision of an independent DSMB comprised of Drs. [name] (chair); [name] and [name]. All DSMB members have extensive experience in either clinical trials and/or management of HIV or HIV prevention experience. The DSMB is responsible for the ongoing review of CHP research and for making recommendations concerning the continuation, modification, and termination of the study.

Appendix A (CHTC Training Manual and Protocol)

- For Full Manual (142 pages) for CHTC please follow the Link:

<https://www.cdc.gov/globalaids/resources/prevention/docs/2014docs/chtc-participant-manual.pdf>

Step 1

Introduce yourself	Hello, my name is ____, and I will be your HIV testing counselor for your session today.
Explain CHTC	
Today, you'll be completing an HIV test together, you will receive your results together, which means you'll hear each others' test results. And you will have the opportunity to discuss how you guys handle HIV risk in your relationship together.
 
(OPTIONAL) We think of CHTC as being "forward looking." In other words, I'm not going to ask you to discuss your sexual history, instead we'll focus on how you guys want to handle HIV risk going forward.

Benefits of CHTC	The benefit of completing CHTC is that you'll both know each other's status and can make plans to keep each other healthy.
Conditions of CHTC	
 1. Agree to discuss any concerns you have about HIV and the ways you'll handle HIV risk going forward. 2. Agree to receive your results together as a couple. 3. Agree to handle disclosure decisions together.
Roles/Responsibilities	
Because CHTC is a bit different from individual testing, I would like to take just a minute to talk about what is expected of you as individuals and as a couple during the session. The couples who get the best out of this experience are the ones who agree to...
 
Some couples think of these as ground rules.
 
 1. Participate equally 2. Listen and respond to one another 3. be respectful, open and honest 4. be understanding and supportive
Overview of procedures	
I'd like to tell you about how the session typically proceeds
 
 1. We'll complete the HIV test itself 2. While the test develops, we'll talk about your relationship and what brought you in for testing together. 3. We'll discuss HIV risk concerns and any agreements you have about sex. 4. We'll review your HIV test results. 5. I'll provide any information you'd like about results and risk management and we'll discuss your agreement in light of your results today. 
Any questions?

Obtain concurrence	How does that sound? Are you both comfortable continuing with the session?

Step 2

Explain the test	We use a finger prick test here. I'll prick your finger with a small needle and draw a small amount of blood. We'll then wait 20 minutes for the test to develop.
Explain individual results	
The test looks for HIV antigens and antibodies to the HIV virus
 
A positive test result means antibodies or antigens were detected in your blood. Antigens stimulates the immune system to produce antibodies, so this test is better at picking up recent infections.
 
 1. The test we use is highly accurate, which means it is highly likely that you have HIV if the test comes back positive. 2. When a positive test result occurs, a confirmatory test is done. We do not offer confirmatory testing services however, we have agreements with community partners who provide confirmatory testing and linkage to care for anyone who receives a preliminary positive HIV test result here at PRIDE. 
An HIV-negative test result means that the test did not detect HIV antibodies or antigen.
 
 1. While our tests are very accurate for detecting antibodies, there is a "window period." It takes a while for your body to produce antibodies to HIV, so we cannot reliably detect an infection that occurred in the past 3 months, but if your test comes back antigen positive you might have been infected recently but the virus is not settled yet in your system, that's why we offer a confirmatory test option for that type of results and the turnover it's 24 hours approx and requires 1 blood vial to send the laboratory. 2. We recommend to all couples that you be retested in 3 months. 3. For couples who are considering stopping condom use, we generally recommend they continue using condoms until they are retested.
Explain couple results	
So there are three possible results that you could have as a couple.
 
 1. You could both be HIV negative 2. You could both be HIV positive 3. Or your results could be different. One of you could be HIV negative and the other HIV positive.
Obtain consent to test	
Collect specimen	

Step 3

Explore couple's relationship

While the test develops, we have some time to talk about the two of you.

1. Tell me a bit about your relationship.
(OPTIONAL) When and how did you meet?
(OPTIONAL) Do you live together now?
2. What is most important to you about this relationship?
3. When you look ahead in this relationship, what do you envision?

Summarize and reflect strengths

Step 4

Why CHTC?

What brought you in to receive HIV testing as a couple?

Feelings on CHTC?

How do you both feel about getting tested (and receiving your results) together?

Current risk management

Assess current risk management practices in the couple
2. How do you guys handle or manage HIV risk?

HIV risk concerns

Again, my goal here is not to "look back" or review sexual history, but I am curious, right now, as of today:
1. What effect has HIV risk or thinking about HIV had on you guys as a couple?
2. What concerns do you have about HIV and the risk for HIV in your relationship.
3. How concerned are you both about the results you might receive today?

Summarize

Step 5

Explain agreements

Many couples have agreements or understandings about how they have sex together and with partners outside their relationships. Some couples may be monogamous or exclusive. Some couples may be open, which means one or both partners may have sex with other people. Other couples go for something in the middle.

Explore agreement

What agreements or understandings do the two of you have around sex?
If yes, explore the agreement
1. What does it look like?
2. Where do condoms fit in?
If no, normalize and clarify

It's ok to not have an agreement. Many couples don't. Most couples find it useful to develop an agreement. It can help guys get on the same page, build trust, and reduce risk.

1. What kind of an agreement do you think would work for you guys?
2. What kinds of "rules" or "terms" would you like to establish if you were to put an agreement in place?
3. Where would condoms fit into this agreement?

Summarize agreement

Obtain concurrence

Agreement and risk

Whatever agreement you guys choose is ultimately up to you. With any couple, I ask them to think about a couple of things related to HIV risk.

1. In what ways does this agreement reduce your risk for HIV?
2. Where might HIV risk occur in this agreement?
3. If someone were to step outside of the agreement (and even in the best relationships, that's not impossible), what would you want to know and how would you want to be told?

Step 6

Confirm ready

I have your test results. Are you ready to receive them together?

Provide results

Say one of the following:

1. Your results are the same, you are both HIV negative
2. Your results are the same, you are both HIV positive.
3. Your results are different, (look at positive partner) and your result is HIV positive.

Step 7

Explore reaction to result

What thoughts, if any, do you have about these results?

[FOR CONCORDANT NEGATIVE COUPLES]

Risk Prevention Planning

Revisit (Summarize) Sexual agreement and existing HIV risk reduction strategies

Given your result today, what if anything do you guys plan to do to manage HIV risk going forward?

1. Revisit condom use if relevant and not addressed previously
2. Revisit PrEP if relevant and not addressed previously
 - a. What have you heard about PrEP?
 - b. Provide information as needed, confirm that couples know where they could access PrEP if they wanted to
 - c. How useful do you guys think PrEP would be for you personally?

What have you heard about U=U?

Retesting

[IF NO EXPOSURE CONCERNS WERE DISCLOSED] "We recommend that all couples get retested in 6 months, just as part of routine sexual-health care."

[IF SPECIFIC EXPOSURE CONCERNS WERE DISCUSSED] "For any couple, we recommend they get retested routinely every 6 months, just as a part of routine sexual-health care. For you guys, we recommend that you get retested in 3 months, just as a routine follow up given the exposure you discussed earlier."

[FOR COUPLES WHERE ONE OR BOTH PARTNERS ARE HIV POSITIVE]

Connection to care

[for positive member(s)]

1. Allow the participant to express his feelings about this result.

2. Remind the participant of confirmatory testing options and ask, "What would you like to do from here?"

3. Plan for connection to care:

If the participant does not wish to be taken for confirmatory testing: Discuss a plan for confirmatory testing access.

If the participant wishes to be taken for confirmatory testing: Complete step 8 and proceed with post-test protocol

4. Discuss self-care, including sexual risk reduction and emotional/physical health care referrals

Risk Prevention Planning

Revisit (Summarize) Sexual agreement and existing HIV risk reduction strategies

Given your result today, what if anything do you guys plan to do to manage HIV risk going forward?

[For discordant couples]

1. Revisit condom use if relevant and not addressed previously

2. Revisit PrEP if relevant and not addressed previously

a. What have you heard about PrEP?

b. Provide information as needed, confirm that couples know where they could access PrEP if they wanted to

c. How useful do you guys think PrEP would be for you personally?

Retesting [for negatives]

If you have not already, make sure to check in with the **negative partner** in a discordant relationship.

1. How are you feeling?

2. What do you need right now?

3. What are your thoughts, hopes, or concerns about PARTNER NAME's next steps.

Discuss the need for retesting

"For any couple, we recommend they get retested routinely every 6 months, just as a part of routine sexual-health care. For you guys, we recommend that you get retested in 3 months, just as a routine follow up given the exposure you discussed earlier."

Step 8

Provide referrals

All couples should get the We Test referral sheet

Specifically point out:

1. Locations for HIV testing (though it likely will not be CHTC)
2. PrEP providers (for any couple with at least one negative result)
3. The presence of general health, mental health, as well as sexual health providers on the list

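### The printed couples HIV testing script gives concordant-negative couples who raise no exposure concern two retest intervals, 3 months and then 6, with nothing linking them

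*Protocol*

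**What the plan says.** Protocol Section 4.7.1 places couples HIV testing in session 3 of both conditions. Appendix A prints the counsellor's script.

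In Step 2, before the blood is drawn, the counsellor explains what a negative result means. The couple hears that "we cannot reliably detect an infection that occurred in the past 3 months" and then, as the next numbered item, "We recommend to all couples that you be retested in 3 months". A third item advises couples who are thinking of giving up condoms to keep using them until the retest.

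In Step 7, after the results, there are three retest lines:

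- Concordant-negative couple, no exposure concern disclosed: "We recommend that all couples get retested in 6 months, just as part of routine sexual-health care".
- Concordant-negative couple, specific exposure discussed: "For any couple, we recommend they get retested routinely every 6 months, just as a part of routine sexual-health care", followed by a 3-month retest for this couple, "just as a routine follow up given the exposure you discussed earlier".
- Negative partner, in the branch for couples with at least one positive result: the same two-part wording, ending on 3 months.

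**The concern.** Step 2 and the Step 7 no-exposure line are both addressed to all couples, yet they give different intervals. One couple hears both in one session, and the 6-month figure comes last, at the point where the result is known and plans are made.

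What is at stake is safety advice to participants. Section 3.1 enrols couples in which either partner reports recent condomless sex with a casual partner, or with a non-monogamous or serodiscordant main partner. The schedule in Section 4.4 marks HIV testing at session 3 only, so the study itself offers no later HIV test to catch an infection missed that day. The ambiguity also reaches the condom advice in Step 2: if the date of the retest is unclear, so is the date until which condoms should be continued.

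**Working it through.** The plan gives no figure to reproduce. The check sets the retest lines of Appendix A side by side.

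| Place in script | Who hears it | 3 months stated | 6 months stated | Interval heard last |
|---|---|---|---|---|
| Step 2 | every couple | yes | no | 3 months |
| Step 7, concordant-negative, no exposure concern | that couple | no | yes | 6 months |
| Step 7, concordant-negative, exposure discussed | that couple | yes | yes, as routine | 3 months |
| Step 7, at least one positive result | the negative partner | yes | yes, as routine | 3 months |

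**Count.** Of the 3 Step 7 lines, 2 include the 3-month retest and 1 omits it. Only the line that omits it conflicts with Step 2.

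**Gap.** 6 − 3 = 3 months between the two recommendations that the affected couple hears.

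**Does an undisclosed exposure plausibly fall in the window?** Inputs: qualifying sex in the 30 days before screening (Section 3.1); sessions about weekly, with session 1 ideally at baseline, so session 3 is about day 14 (Sections 4.4 and 4.5); and a session window that closes at day 45 (Section 4.4). The gap from screening to baseline is not stated; call it g days.

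- Usual schedule: the qualifying act is between 0 + 14 = 14 and 30 + 14 = 44 days old at session 3, plus g.
- Latest schedule: at most 30 + 45 = 75 days, plus g.
- Taking 3 months as 90 days, as the follow-up windows do, the act is inside the script's own window whenever g is below 90 − 75 = 15 days, even on the latest schedule. On the usual schedule it is inside whenever g is below 90 − 44 = 46 days.

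So, unless g is long, the behaviour that made a couple eligible usually lies within the period that Step 2 says the test cannot reliably cover.

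**Does the branching reliably pick out such couples?** The Step 7 branch depends on what was disclosed. Step 4 has the counsellor say that the aim is not to go over past sexual behaviour, and Step 1 has an optional line to the same effect. A couple can therefore reach the no-exposure line without being exposure-free.

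**The case against.** The strongest defence is that the two lines do different jobs. Step 2 concerns the window period of today's test, and the Step 7 line is labelled routine care. A 3-month retest and a 6-month routine test can both be right, and only a linking phrase is missing. This stands in part, but the structure of Step 7 works against it. There a concordant-negative couple hears 3 months only if an exposure was discussed, which is a different rule from Step 2, where everyone hears it.

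Other mitigating points also stand:

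- The test detects antigen as well as antibody, and Step 2 adds "so this test is better at picking up recent infections".
- Step 5 asks "Where might HIV risk occur in this agreement", which may bring an exposure out and move the couple to the 3-month line.
- For CHP session 3, Section 5.1.1 lists "CVCT or individual HIV testing and counseling", so not every CHP couple need hear this script.
- Step 8 gives every couple a referral sheet that includes HIV testing sites.
- Appendix A links a 142-page manual, and Section 5.3 requires training and mock sessions before clearance. Counsellors may have been taught how the two lines relate. The manual was not available, so the finding covers the printed script only.

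A reader might infer more than this supports. One inference is that infections would be detected 3 months late. That figure is the gap between two recommendations; an actual delay also needs an infection missed by the test and a couple that acts on the later line. Another is that the affected group is small, or large; no document gives its size. A third is that all of the Step 7 retest wording is faulty, but the other two lines already end on 3 months and agree with Step 2.

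**Conclusion.** The point holds as a minor internal inconsistency in participant-safety text. It is not a design choice that reasonable people might defend either way: the printed script gives one group of couples two intervals and does not say how they relate.

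Confidence in the wording conflict is high. Its size is 1 of 3 Step 7 lines and a 3-month difference in advice. How many of the planned 50 couples reach that line, and whether any detection would be delayed, cannot be determined from the documents.

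A reader might also infer that the trial's results are at risk. They are not: testing is placed in session 3 of both conditions, HIV test results do not enter the models described in the SAP, and endpoints, the arm comparison and the analysis are unaffected.

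The conclusion assumes that counsellors follow the script as printed and that no unseen training material reconciles the two lines.

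**What to change.** Change only the Step 7 line for concordant-negative couples with no disclosed exposure concern, subject to clinician sign-off. Suggested wording: *We recommend that every couple test again in 3 months, because today's test may miss a recent infection, and every 6 months after that as routine sexual-health care.* This matches Step 2, keeps the routine message, and gives the condom advice a clear end date. Qualifying Step 2 instead, so that 3 months applies only after an exposure, would also remove the mismatch. It fits poorly with the window-period statement there and with a script that does not review past behaviour.

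The cost is one line of script and a staff re-briefing, with no new procedure or data. Section 4.7.1 notes that specimen collection was suspended on 15 March 2020, so the benefit is to in-person use or later reuse of the script.

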- **HIV testing.** HIV testing will be conducted in the context of couples' HIV testing conducted in session 3 of both conditions. Testing will be performed using the Alere Determine Ab/Ag Testing Kit[®]. An RA trained in CHTC will utilize a lancet to gather a sample of blood from the participant's finger. This blood is then collected with a capillary tube and placed on the designated area of the test strip, and then a drop of chase buffer is added to the testing area to culture. Test results are available in 20 minutes and delivered to participants immediately

during the couples HIV testing and counselling session. For additional information on HIV confirmatory testing and reporting see Attachments.

***NOTE: Due to COVID-19, collection of biological specimen data was suspended on 3/15/2020. All follow-up assessments completed after that date were conducted remotely via Zoom and online survey administration via Qualtrics.

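### Step 6 of the couples HIV testing script announces a reactive rapid result as HIV positive without saying that it is preliminary and still needs confirmation

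*Protocol*

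**What the plan says.** Section 4.7.1 of the Protocol places HIV testing in Session 3 of both arms, by finger-stick rapid test: "Test results are available in 20 minutes and delivered to participants immediately". The schedule in section 4.4 lists no other HIV test.

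Appendix A scripts the session.

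- **Step 2, before the test.** The counsellor says that a positive test makes infection highly likely and that a confirmatory test follows. On where this happens the script says "We do not offer confirmatory testing services however", and it then points to community partners who provide confirmation and "linkage to care for anyone who receives a preliminary positive HIV test result here at PRIDE". A later line of Step 2 describes an optional confirmatory test for antigen-positive results, with a blood vial sent to a laboratory and a turnaround of about 24 hours. Step 2 also lists the possible couple results, among them "You could both be HIV positive".
- **Step 6, delivery of results.** The instruction is "Say one of the following". Of the three statements offered, the second is "Your results are the same, you are both HIV positive" and the third is "Your results are different, (look at positive partner) and your result is HIV positive".
- **Step 7, after delivery.** Where one or both partners are positive, the counsellor lets the man express his feelings, reminds him of the confirmatory options, and plans access to confirmation whether or not he wishes to be taken for it.

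**The concern.** At Step 6 a new reactive result is about 20 minutes old and cannot yet have been confirmed. Step 2 has just described such a result as preliminary. Step 6 nevertheless prescribes words that sound settled, and both partners hear them at the same moment.

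What is at stake is how one man and his partner understand his status between the announcement and the confirmatory result. If he is infected, the label is premature but not false. If the result is a false reactive, the couple has been told something untrue about him, and joint disclosure makes that harder to take back.

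**Working it through.** The plan gives no figure on this point, so the check is mainly a comparison of texts.

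**1. Is confirmation outstanding when Step 6 is spoken?** Yes, for any new reactive result. Section 4.7.1 has results delivered at 20 minutes. Step 2 sends confirmation to community partners, or to a laboratory with a turnaround of about a day. The two Step 2 lines sit awkwardly together, since one says that the site does not offer confirmation and the other offers an option, but on either reading the answer arrives after the session. Step 7 still asks whether the man wishes to be taken for confirmation, which agrees with this.

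**2. What do the three Step 6 statements assert?**

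| Statement | Form | Says preliminary? |
|---|---|---|
| 1. Both negative | Status | Not applicable |
| 2. Both positive | Status (what the men are) | No |
| 3. Discordant | Result (what the test showed) | No |

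Two of the three carry the unqualified label. Item 2 is the stronger case. Item 3 can be read literally as a report of a test result.

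**3. Whom does item 2 cover?** Section 3.1 requires one partner to be HIV-negative and allows the other to be positive. A both-positive announcement therefore normally means either two new reactive results, or one known infection and one new reactive result. How often known-discordant couples reach item 2 is unclear. Section 4.7.1 describes couples testing in both arms, while the CHP session table in 5.1.1 allows individual testing and its footnote limits testing to HIV-negative participants.

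**4. Is the loose label confined to Step 6?** No. The Step 2 list of couple results uses it for both the both-positive and the discordant outcome.

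**5. Scale, for illustration only.** The documents give no test accuracy and no prevalence of undiagnosed infection. Assume specificity s of 99.0% to 99.9%, undiagnosed infection p of 0.5% to 2%, sensitivity of 100%, and all men who enter as HIV-negative tested. With 50 couples, M = 50 to 100 such men. The false-reactive probability is f = (1 − p)(1 − s).

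- New reactive men, M(p + f): from 50 × (0.005 + 0.000995) = 0.30 to 100 × (0.02 + 0.0098) = 2.98.
- Share of these that are false, f/(p + f): from 0.00098/0.02098 = 0.047 to 0.00995/0.01495 = 0.666.

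Under these inputs the announcement would concern roughly zero to three newly reactive men in the whole trial. These values are not bounds, because a lower specificity would raise them. The wording point does not depend on them.

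**The case against.** The best defence is that the term is explained before it is used. Step 2 tells the couple what a positive test means, that it makes infection likely rather than certain, and that a confirmatory test follows. Step 6 presents its statements as test results, and Step 7 returns to confirmation soon afterwards. On this view only the placing of the reminder is in dispute. Much of this stands, and it is why the point is minor. It does not change the words that Step 6 prescribes, and item 2 goes beyond reporting a result.

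The documents on confirmatory testing that section 4.7.1 calls Attachments, the post-test protocol named in Step 7 and the 142-page CHTC manual are not in the text reviewed and may add guidance on delivery. That also stands as a limit, although Step 6 as written already supplies the words to be spoken.

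A reader might infer more than the documents support:

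- *That confirmatory testing is missing.* It is explained in Step 2 and planned in Step 7.
- *That Step 6 uses language foreign to Step 2.* This is only partly so, because the Step 2 list of couple results uses the same label.
- *That item 2 must always include a new, unconfirmed result.* The schedule shows no HIV test at entry, and the session window runs to day 45. A man could be misclassified at entry or diagnosed elsewhere before Session 3.
- *That a couple called both positive loses its prevention counselling.* The Step 7 condom and PrEP prompts are tagged for discordant couples, and the Step 8 PrEP-provider pointer needs at least one negative result. But Step 2 already says "For couples who are considering stopping condom use, we generally recommend they continue using condoms until they are retested", Step 5 raises condoms and risk with every couple, and the Step 7 review of the agreement and its item on sexual risk reduction still apply. The effect on branching is too rare and too dependent on assumptions to carry weight.

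**Conclusion.** The point holds as a minor matter of participant safety. Step 6 tells the counsellor to announce a reactive rapid result as HIV positive without a qualifier, although by the script's own account the result is preliminary and confirmation comes later. The fault is clearest in the both-positive statement, weaker in the discordant one, and shared by the Step 2 list of couple results.

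The conclusion rests on the texts of Steps 2, 6 and 7 and on the 20-minute delivery in section 4.7.1. It assumes that no unseen attachment replaces the Step 6 wording. It does not rest on the illustrative rates. It has no bearing on endpoints or analysis: the SAP's text refers to drug use and to CAS with casual partners and makes no use of the HIV test result.

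**What to change.** - In Step 6, items 2 and 3, and in items 2 and 3 of the Step 2 list of couple results, say *preliminary positive; a confirmatory test is needed* for any newly reactive result. Leave an already known infection labelled as such.
- Until confirmation, do not route a newly reactive partner through Step 7 as a confirmed positive. Keep the condom prompt for that couple.
- Leave the Step 7 connection-to-care items unchanged.

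The cost is a script edit and brief counsellor retraining, with no added test, staff or visit. The downside is a slightly softer label that could reduce urgency, which the unchanged connection-to-care items should offset. The SAP, last updated in June 2021, describes its analyses in the past tense, so the benefit may fall mainly on later use of this script.
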